9.7 Data analysis

The analysis will be based on descriptive statistics: frequencies and percentages will be calculated to the variables of interests, continuous and count variables will be described using mean (\pm standard deviation), proportions, median (quartiles) and minimum and maximum values. 95% confidence intervals will be computed for descriptive variables. The following outcomes will be assessed:

- Describe the three study cohorts i.e. patients prescribed with rivaroxaban, dabigatran, apixaban by baseline characteristics, use of medications, comorbidities and healthcare utilization services

(see all the variables in section 9.3) among the three study cohorts and contrast them with the baseline characteristics of patients in clinical trials.

- Use of study medications: Dose at first Rx, dose posology, duration of treatment (time on index medication), discontinuation, switch to another study drug .
- To assess the proportion of patients that are dosed in accordance and non-accordance to label, in study population and in subset of patients with renal impairment
- Contrasting patient characteristics of those prescribed DOACs with the corresponding characteristics in patients participating in clinical trials.

Table 1: Dosing of each study drug in the study population.

	Rivaroxaban	Apixaban	Dabigatran
Low dose Renal impairment Other indication to reduce the dose Non- accordance to label			
Standard dose incl.documented renal impairment			
All			

- Use of medication before index date will be categorized as:
 - Concurrent use (when the drug supply lasts until index date or is prescribed at index-date)
 - Recent (when the drug supply ends 1-30 days before index date)
 - Past use (when the drug supply ends 31-365 days before index date)
 - Non-use: no use in year before index date

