Annex 3. Additional information

List of Read Codes

Table S1.

Multilex code	BNF-code	Generic Name	ATC	ATC name	BCD	BCD name
53246979	02.08.02.00	Apixaban 5mg tablets	B01A	ANTITHROMBOTIC AGENTS	60396	APIXABAN
53247979	02.08.02.00	Apixaban 5mg tablets	B01A	ANTITHROMBOTIC AGENTS	60396	APIXABAN
81167998	02.08.02.00	Apixaban 2.5mg tablets	B01A F02	APIXABAN	60396	APIXABAN
81168998	02.08.02.00	Apixaban 2.5mg tablets	B01A F02	APIXABAN	60396	APIXABAN
81214998	02.08.02.00	Dabigatran etex150mg cap	B01A E07	DABIGATRAN ETEXILATE	60278	DABIGATRAN
81215998	02.08.02.00	Dabigatran etexilate 150mg caps	B01A E07	DABIGATRAN ETEXILATE	60278	DABIGATRAN
83971998	02.08.02.00	Dabigatran etexilate 110mg caps	B01A E07	DABIGATRAN ETEXILATE	60278	DABIGATRAN
83972998	02.08.02.00	Dabigatran etexilate 75mg caps	B01A E07	DABIGATRAN ETEXILATE	60278	DABIGATRAN
83973998	02.08.02.00	Dabigatran etexilate 75mg caps	B01A E07	DABIGATRAN ETEXILATE	60278	DABIGATRAN
83974998	02.08.02.00	Dabigatran etexilate 110mg caps	B01A E07	DABIGATRAN ETEXILATE	60278	DABIGATRAN
59454978	02.08.02.00	Rivaroxaban 2.5mg tablets	B01A F01	RIVAROXABAN	60320	RIVAROXABAN
60767979	02.08.02.00	Rivaroxaban 20mg tablets	B01A F01	RIVAROXABAN	60320	RIVAROXABAN
60768979	02.08.02.00	Rivaroxaban 20mg tablets	B01A F01	RIVAROXABAN	60320	RIVAROXABAN
60769979	02.08.02.00	Rivaroxaban 15mg tablets	B01A F01	RIVAROXABAN	60320	RIVAROXABAN
60770979	02.08.02.00	Rivaroxaban 15mg tablets	B01A F01	RIVAROXABAN	60320	RIVAROXABAN
80953998	02.08.02.00	Rivaroxaban 20mg tablets	B01A F01	RIVAROXABAN	60320	RIVAROXABAN
80954998	02.08.02.00	Rivaroxaban 20mg tablets	B01A F01	RIVAROXABAN	60320	RIVAROXABAN
80955998	02.08.02.00	Rivaroxaban 15mg tablets	B01A F01	RIVAROXABAN	60320	RIVAROXABAN
80956998	02.08.02.00	Rivaroxaban 15mg tablets	B01A F01	RIVAROXABAN	60320	RIVAROXABAN
83418998	02.08.02.00	Rivaroxaban 10mg tablets	B01A F01	RIVAROXABAN	60320	RIVAROXABAN
83425998	02.08.02.00	Rivaroxaban 10mg tablets	B01A F01	RIVAROXABAN	60320	RIVAROXABAN

Table S2:

Operational definitions for subpopulations:

Non-valvular Atrial Fibrillation (NVAf)	Patients with a record of Atrial fibrillation (AF) any time prior index date or within the 2 weeks after the index date, and free of valvular replacement or mitral stenosis (see table codes below) prior to index date or 2 weeks after index-date

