Renal Impairment	We will obtain eGFR values from creatinine values using the MDMR (1) or CDK-EPI (2) formula. Furthermore we will define four levels of decreasing severity of 
 - severe renal impairment (defined as eGFR < 30 ml/min/1.73m²) or READ code indicating renal dialysis or kidney transplant - moderate renal impairment (defined as eGFR 30–44 ml/min/1.73m²) - mild renal disease (45–59 ml/min/1.73m²)

(1) Modification of Diet in Renal Disease equation (MDMR) formula to calculate the eGFR, expressed in ml per minute

$$eGFR = 186 \times (\text{Creat} / 88.4)^{-1.154} \times (\text{Age})^{-0.203} \times (0.742 \text{ if female})$$

(2) CDK-EPI Formula: $eGFR = 141 * \min(\text{Scr}/\kappa, 1)^\alpha * \max(\text{Scr}/\kappa, 1) - 1.209 * 0.993 \text{Age} * 1.018 \text{ [if female]} * 1.159 \text{ [if black]}$

Scr: serum creatinine (mg/dL)
κ : 0.7 for females and 0.9 for males
α: 0.329 for females and 0.411 for males
min : the minimum of *Scr/κ* or 1
max : the maximum of *Scr/κ* or 1.

Table S3- AF READ codes

READ	Description
3272.00	ECG: ATRIAL FIBRILLATION
3273.00	ECG: ATRIAL FLUTTER
3274.00	ECG: PAROXYSMAL ATRIAL TACHY.
7936A00	IMPLANT INTRAVENOUS PACEMAKER FOR ATRIAL FIBRILLATION
G570.00	PAROXYSMAL SUPRAVENTRICULAR TACHYCARDIA
G570000	PAROXYSMAL ATRIAL TACHYCARDIA
G573.00	ATRIAL FIBRILLATION AND FLUTTER
G573000	ATRIAL FIBRILLATION
G573100	ATRIAL FLUTTER
G573200	PAROXYSMAL ATRIAL FIBRILLATION
G573z00	ATRIAL FIBRILLATION AND FLUTTER NOS
14AN.00	H/O: ATRIAL FIBRILLATION
212R.00	Atrial fibrillation resolved
662S.00	Atrial fibrillation monitoring
6A9..00	Atrial fibrillation annual review
9hF..00	Exception reporting: atrial fibrillation quality indicators
9hF1.00	Excepted from atrial fibrillation qual indic: Inform dissent
9Os..00	Atrial fibrillation monitoring administration
9Os0.00	Atrial fibrillation monitoring first letter
9Os1.00	Atrial fibrillation monitoring second letter
9Os2.00	Atrial fibrillation monitoring third letter
9Os3.00	Atrial fibrillation monitoring verbal invite
9Os4.00	Atrial fibrillation monitoring telephone invite
G573300	Non-rheumatic atrial fibrillation

Table s4 READ Codes for mitral stenosis (to exclude from AF patients)

READ	Description
G11..11	Rheumatic mitral valve disease
G110.00	Mitral stenosis
G110.11	Rheumatic mitral stenosis
G112.00	Mitral stenosis with insufficiency
G112.12	Mitral stenosis with incompetence

G112.13	Mitral stenosis with regurgitation

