14S4.00	H/O: heart valve recipient
14T3.00	H/O: artificial heart valve
SP00200	Mechanical complication of heart valve prosthesis
SP00400	Infect and inflammatory reaction due to cardiac valve pros
SyuK611	[X] Embolism from prosthetic heart valve
TB01200	Implant of heart valve prosthesis + complication, no blame
ZV42200	[V]Heart valve transplanted
ZV43300	[V]Has artificial heart valve
ZV45H00	[V]Presence of prosthetic heart valve
ZVu6e00	[X]Presence of other heart valve replacement

Table S6. Read codes of Dialysis (renal Impairment)

Read	Description
14V2.00	H/O: renal dialysis
14V2.11	H/O: kidney dialysis
4I29.00	Peritoneal dialysis sample
4N3..00	Peritoneal dialysis fluid cell count
4N4..00	Dialysis fluid potassium level
4N5..00	Dialysis fluid sodium level
7A60600	Creation of graft fistula for dialysis
7A61900	Ligation of arteriovenous dialysis fistula
7A61A00	Ligation of arteriovenous dialysis graft
7L1A.11	Dialysis for renal failure

7L1A000	Renal dialysis
7L1A011	Thomas intravascular shunt for dialysis
7L1A100	Peritoneal dialysis
7L1A200	Haemodialysis NEC
7L1A400	Automated peritoneal dialysis
7L1A500	Continuous ambulatory peritoneal dialysis
7L1A600	Peritoneal dialysis NEC
7L1B.11	Placement ambulatory dialysis apparatus - compens renal fail
7L1B000	Insertion of ambulatory peritoneal dialysis catheter
7L1B100	Removal of ambulatory peritoneal dialysis catheter
7L1B200	Flushing of peritoneal dialysis catheter
7L1C000	Insertion of temporary peritoneal dialysis catheter
7L1f000	Extracorporeal albumin haemodialysis
8882.00	Intestinal dialysis
SP05613	[X] Peritoneal dialysis associated peritonitis
SP06B00	Continuous ambulatory peritoneal dialysis associated perit
TA02.00	Accid cut,puncture,perf,h'ge - kidney dialysis/oth perfusion
TA02000	Accid cut,puncture,perf,h'ge - kidney dialysis
TA02011	Accidental cut/puncture/perf/haem'ge during renal dialysis
TA12000	Foreign object left in body during kidney dialysis
TA12011	Foreign object left in body during renal dialysis
TA22000	Failure of sterile precautions during kidney dialysis
TA22011	Failure of sterile precautions during renal dialysis
TA42000	Mechanical failure of apparatus during kidney dialysis
TA42011	Mechanical failure of apparatus during renal dialysis
TB11.00	Kidney dialysis with complication, without blame
TB11.11	Renal dialysis with complication, without blame
U611200	[X]Foreign obj accid left body dur kidney dialys/oth perfus
U612200	[X]Failure sterile precautions dur kidney dialys/other perf

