U641.00	[X]Kidny dialysis caus abn reac pt/lat comp no misad at time
Z131500	Warming patient with warm haemodialysis
Z131600	Warming patient with warm peritoneal dialysis
Z1A2.00	Haemodialysis training
Z1A2.11	HD - Haemodialysis training
Z919.00	Care of haemodialysis equipment
Z919100	Priming haemodialysis lines
Z919200	Washing back through haemodialysis lines
Z919300	Reversing haemodialysis lines
Z91A.00	Peritoneal dialysis bag procedure
Z91A100	Putting additive into peritoneal dialysis bag
ZV45100	[V]Renal dialysis status

ZV56.00	[V]Aftercare involving intermittent dialysis
ZV56000	[V]Aftercare involving extracorporeal dialysis
ZV56011	[V]Aftercare involving renal dialysis NOS
ZV56100	[V]Preparatory care for dialysis
ZV56y00	[V]Other specified aftercare involving intermittent dialysis
ZV56y11	[V]Aftercare involving peritoneal dialysis
ZV56z00	[V]Unspecified aftercare involving intermittent dialysis
4N...00	Dialysis fluid examination
4N0..00	Dialysis fluid urea level
4N1..00	Dialysis fluid creatinine level
4N2..00	Dialysis fluid glucose level
SP01500	Mechanical complication of dialysis catheter
Z131400	Warming patient by dialysis therapy
Z132800	Cooling patient using cool peritoneal dialysis
Z1A..00	Dialysis training
Z1A1.00	Peritoneal dialysis training
Z1A1.11	PD - Peritoneal dialysis training
Z919400	Recirculation of the dialysis machine
ZVu3G00	[X]Other dialysis

Table S7. Read codes of Kidney transplant (renal Impairment)

Read	Description
7B00.00	Transplantation of kidney
7B00000	Autotransplant of kidney
7B00100	Transplantation of kidney from live donor
7B00111	Allotransplantation of kidney from live donor
7B00200	Transplantation of kidney from cadaver
7B00211	Allotransplantation of kidney from cadaver
7B00300	Allotransplantation of kidney from cadaver, heart-beating
7B00400	Allotransplantation kidney from cadaver, heart non-beating
7B00500	Allotransplantation of kidney from cadaver NEC
7B00y00	Other specified transplantation of kidney
7B00z00	Transplantation of kidney NOS
7B01500	Transplant nephrectomy
7B01511	Excision of rejected transplanted kidney
7B06300	Exploration of renal transplant
7B0F.00	Interventions associated with transplantation of kidney
7B0F100	Pre-transplantation of kidney work-up, recipient
7B0F200	Pre-transplantation of kidney work-up, live donor
7B0F300	Post-transplantation of kidney examination, recipient
7B0F400	Post-transplantation of kidney examination, live donor

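### Table S2 lets any dialysis or kidney-transplant Read code set 'severe renal impairment', with no time window and no precedence for a measured eGFR

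*Protocol*

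**What the plan says.** Table S2 (Annex 3) gives the operational definition of renal impairment. The top class is "severe renal impairment (defined as eGFR < 30 ml/min/1.73m²"), followed by a second criterion: "or READ code indicating renal dialysis or kidney transplant". The next class is "moderate renal impairment (defined as eGFR 30–44 ml/min/1.73m²"), and mild disease is eGFR 45–59. Both lower classes rest on eGFR alone.

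The codes are in Tables S6 (dialysis) and S7 (transplant), and Annex 3 repeats them as one list under a stage 4 dialysis heading. They include "H/O: renal dialysis" (14V2.00) and the matching history code for a kidney recipient (14S2.00). They also include "Warming patient with warm haemodialysis" (Z131500), further warming and cooling codes (Z131600, Z131400, Z132800), and "Autotransplant of kidney" (7B00000).

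The NVAF row of Table S2 does state a window: "any time prior index date or within the 2 weeks after the index date". The renal row states none. Section 9.3 places eGFR, and ACR where available, before the index date, and its variable table lists eGFR or ACR under a 12-month heading. Neither place mentions dialysis or transplant codes.

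Section 9.7 then uses the group with impaired kidney function for its dosing result: "To assess the proportion of patients that are dosed in accordance and non-accordance to label, in study population and in subset of patients with renal" […]. The third primary objective (section 8.1) asks for the proportion with renal impairment at index and their treatment characteristics.

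**The concern.** A dialysis or transplant code records an event or a history. It is not a measure of kidney function at the index date. A person with a working graft, or one dialysed during a past acute illness, may have an eGFR well above 30 when the anticoagulant is started. Because the two criteria are joined by 'or', the code alone is enough, and such a patient meets the severe definition while also meeting a milder one, or none.

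Two results could be affected. The split by severity is affected whenever a coded patient not on dialysis has eGFR 30 or above. Membership of the renal-impairment subset, and so the third primary objective and the label-accordance result, is affected only when that eGFR is 60 or above, because Table S2 already counts 45–59 as mild disease.

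**Working it through.** The protocol states no figure on this point, so there is none to reproduce. The check applies its own rule and formula to two example patients.

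**Inputs.** Formula (1) under Table S2, for men: eGFR = 186 × (creatinine/88.4)^-1.154 × age^-0.203. Bands from Table S2: severe below 30, moderate 30–44, mild 45–59. The ages and creatinine values are illustrative.

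**Patient A.** Man, 60 years, kidney-transplant code, creatinine 130 µmol/L.
- (130/88.4)^-1.154 = 0.6408 and 60^-0.203 = 0.4355
- eGFR = 186 × 0.6408 × 0.4355 = 51.9
- By eGFR: mild. By Table S2 with the code: severe. He is in the renal subset either way.

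**Patient B.** Man, 72 years, history-of-dialysis code from one past episode, creatinine 85 µmol/L.
- (85/88.4)^-1.154 = 1.0463 and 72^-0.203 = 0.4197
- eGFR = 186 × 1.0463 × 0.4197 = 81.7
- By eGFR: not impaired. By Table S2 with the code: severe. He enters the renal subset only because of the code.

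**How far from the boundary.** Solving formula (1) for creatinine gives 88.4 × (186 × age^-0.203 / eGFR)^(1/1.154). A man of 60 falls below eGFR 30 only above about 209 µmol/L, and a man of 72 only above about 202. Neither patient is a borderline case.

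**Consequence by eGFR, for coded patients not on dialysis at index**

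| Measured eGFR | Class by eGFR | Class by Table S2 | Severity split | Renal subset |
|---|---|---|---|---|
| below 30 | severe | severe | unchanged | unchanged |
| 30–44 | moderate | severe | wrong | unchanged |
| 45–59 | mild | severe | wrong | unchanged |
| 60 or above | none | severe | wrong | wrongly included |

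**Size in the severe band (assumptions only).** Let p be the share of users with such a code, q the share of those with current eGFR of 30 or above and not on dialysis, and s the share of users with true eGFR below 30. Assume p = 0.1–0.5%, q = 60–80%, s = 1–3%.
- Relative overstatement of the severe proportion, p × q / s: from 0.001 × 0.6 / 0.03 = 2.0% to 0.005 × 0.8 / 0.01 = 40%.
- Share of the severe class that is misplaced, p × q / (s + p × q): from 0.0006 / 0.0306 = 2.0% to 0.004 / 0.014 = 28.6%.
- Absolute shift, p × q: 0.06 to 0.4 percentage points of all users.
- For scale, section 9.5 cites 541 + 1589 + 741 = 2,871 naïve users in an earlier study. On that number the shift is 2,871 × 0.0006 = 1.7 to 2,871 × 0.004 = 11.5 patients, against 2,871 × 0.03 = 86 to 2,871 × 0.01 = 29 with true eGFR below 30.

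**Size in the overall impaired proportion.** Only coded patients with eGFR 60 or above count. They are a subset of p × q, so under the same assumptions the excess cannot exceed 0.4 percentage points. It is also divided by a larger base, namely everyone with eGFR below 60.

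**The case against.** The two-part definition looks deliberate. The code criterion stands outside the eGFR bracket, and Annex 3 groups the same codes again under one stage 4 heading. For a patient now on dialysis, letting the code override a creatinine-based eGFR is defensible. That stands, and the fix keeps it. It does not extend to transplant recipients or to history-only codes.

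A look-back could be left to an analysis plan, and section 9.3 offers a plausible one. This stands in part: the text never says that a code counts at any date, so a reader who infers an explicit 'ever' rule is reading silence as a rule. Yet the wording in section 9.3 covers eGFR and ACR, not codes. A 12-month window would also not settle the matter, because a history code entered within it would still count and no precedence for eGFR would be set. Table S2 states an operative rule and supplies its codes. The fault is in that rule, so this is more than detail left for later.

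Three stronger readings are tempting and lack support. The third primary objective does not ask for results by severity; the levels appear only in Annex 3. Section 9.7 and its Table 1 use one undivided renal-impairment group, so a coded patient with eGFR 30–59 belongs there with or without the code. And the protocol does not say that label accordance is judged by the Table S2 severity class, so one cannot conclude that every misplaced patient's dose would be assessed against the wrong kidney function.

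Finally, nothing shows that the warming, cooling or autotransplant codes occur in this cohort. That is fair: removing them is list cleaning, and the transplant and history codes are the core of the point.

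**Conclusion.** The point holds in a limited form. As written, Table S2 places transplant recipients with a working graft and past-dialysis patients in the severe class whatever their measured eGFR. For coded patients not on dialysis, an eGFR of 30–59 distorts the severity split only. An eGFR of 60 or above also brings them wrongly into the subset used for the third primary objective and the label-accordance result.

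The size cannot be taken from the documents, which give no code frequencies. It is probably small in the whole cohort, but it falls in what is likely a small severe band, and smaller still once split by drug. The relative range of 2% to 40% is assumption only. A reader might take it as the error in the proportion with renal impairment, but it applies to the severe band alone. The two worked patients show that the rule misclassifies; they do not show how often.

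The edit is cheap and should be made before the data are extracted.

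**What to change.** Rewrite the renal row of Table S2 as an ordered rule:

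1. Class as severe any patient with a code showing dialysis ongoing at index, within a stated look-back before the index date (for example 12 months) and with no later transplant.
2. Class everyone else by the last eGFR before index, including transplant recipients and patients with history-only codes.
3. Use a transplant code to set severity only if no eGFR exists.
4. Remove the warming and cooling codes (Z131400, Z131500, Z131600, Z132800) and the autotransplant code (7B00000) from the lists that set severity, including the repeated list later in Annex 3.

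Transplant recipients can be shown as a separate descriptive row if wanted.

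The cost is a wording change, a short code-list edit and a precedence rule in the program, with no new data. The downside is that a few dialysis patients without a recent code would be classed by eGFR alone.

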9.1 Study design

This is a population-based retrospective cohort study designed to assess the characteristics of patients and patterns of drug utilization in new users of DOACs in the UK.

The study enrollement period extends from 1st January 2011 up to last available database extraction (at time of writing, May 2016 in THIN and in CPRD).

Among the source population resulting from the combination of THIN and CPRD databases, we will ascertain three separate cohorts of first-time users of rivaroxaban, apixaban and dabigatran using the date of first prescription (index date) of the respective drug (index drug).

This study will apply a new-users (initiators) design (Ray et al, 2003). New users are individuals starting a study medication for the first time ever recorded in the database. Yet, they may have used the other study medications before index date and therefore classified as non-naïve. New-users without any history of any oral anticoagulant would be classified as naïve.

All patients aged 18 and above and who have been enrolled in the databases for at least 1 year and had their first prescription recorded in the databases at least 1 year ago will be included in source population. A patient will be considered eligible to enter a study cohort as a first-time user of one the study drugs when he or she has a first prescription of the drug recorded during the enrolment period.

Patients who have any record of being prescribed their index drug prior to the enrolment period or who qualify as members of more than one cohort on the same day, will be excluded. If a patient qualifies as first-time user of more than one study drug during the enrolment period, with different index dates, she/he will be assigned to the cohort of study drug first prescribed during the enrolment period, with the date of this prescription being the index date. (eg mutually exclusive cohorts)

Among the three study cohorts, we will further identify patients with NVAF defined as:-

Patients with a record of Atrial fibrillation (AF) any time prior index date or within the 2 weeks after the index date, and free of valvular replacement or mitral stenosis prior to index date or 2 weeks after index-date

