9.5 Study size

THIN version1605: The prevalence of AF (2011-2016), among patients 18+ and register with GP for at least a year 1.92% (No. of patients with AF= 75784). The prevalence of AF excluding patients with prior Mitral Stenosis or Valvular replacement = 1.89% (N= 74319).

CPRD GOLD database in 2014: authors reported a prevalence AF in all ages was 2.47% in men and 1.56 % in women. ([Bhatnagar](#) et al, 2015).

A study conducted using CPRD by Johnson et al, 2016, identified 541 na ĩve apixaban users, 1589 na ĩve rivaroxaban users, and 741 na ĩve dabigatran users up to October 2014.

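### Table S3, the AF code list, is broader than the NVAF definition it implements: three of its 24 codes name paroxysmal atrial or supraventricular tachycardia, not AF or flutter

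*Protocol*

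**What the plan says.** Section 9.1 first forms three cohorts from any first prescription of rivaroxaban, apixaban or dabigatran in the enrolment period. It then identifies the NVAF patients among them: "Patients with a record of Atrial fibrillation (AF) any time prior index date or within the 2 weeks after the index date", provided they have no valve replacement or mitral stenosis. Annex 3, Table S2, repeats this under "Operational definitions for subpopulations".

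The codes that make up an AF record are in the table headed "Table S3- AF READ codes". Besides codes for fibrillation and flutter, it lists:

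- 3274.00, "ECG: PAROXYSMAL ATRIAL TACHY"
- G570.00, "PAROXYSMAL SUPRAVENTRICULAR TACHYCARDIA"
- G570000, "PAROXYSMAL ATRIAL TACHYCARDIA"

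The exclusions that follow are Table S4 ("READ Codes for mitral stenosis (to exclude from AF patients") and Table S5 for valve replacement. Nothing in the protocol says that the AF definition was meant to cover other supraventricular arrhythmias.

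**The concern.** The text names one condition and the list admits another. Because the cohorts start from any DOAC prescription, Table S1 covers every strength, and no rule excludes users treated for a different indication, the AF list is the only operational check that a patient belongs to the population named in section 8: NVAF patients treated for stroke prevention.

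NVAF membership is the denominator for every primary and secondary end-point in sections 9.1.1 and 9.1.2. Table 1 in section 9.7 is the most exposed. It sorts low-dose patients into renal impairment, another reason to reduce the dose, or non-accordance with the label. A patient without AF would be judged there against a label indication that may not be the reason for treatment.

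**Working it through.** **1. Classify the codes in Table S3 by their own descriptions.**

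| Description names | Codes | Count |
|---|---|---|
| Atrial fibrillation (alone or with flutter) | all others | 19 |
| Atrial flutter only | 3273.00, G573100 | 2 |
| Paroxysmal atrial or supraventricular tachycardia only | 3274.00, G570.00, G570000 | 3 |
| Total | | 24 |

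Removing the last group leaves 24 − 3 = 21 codes. The share 3/24 = 12.5% is a share of codes, not of patients.

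**2. Are the three codes needed to capture paroxysmal AF?** No. Paroxysmal AF has its own code in the same table, G573200. Fibrillation and flutter share the heading G573, while the tachycardia codes G570.00 and G570000 sit under a separate heading, G570.

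**3. Would a later step remove a patient who has only a tachycardia code?**

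- Section 9.1 and Table S2: one record is enough, and no second AF-specific code is required.
- Tables S4 and S5: these remove only mitral stenosis and valve replacement.
- Section 9.2: THIN is preferred for its free text, but no free-text confirmation of AF is described.
- Section 9.6: validation results are among the materials archived for each project, but no validation of the AF diagnosis is described. The ENCePP checklist answers No on whether the validity of endpoint measurement is discussed (item 6.2).
- Section 9.9: the limitations do not mention the point.

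So the answer is no.

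**4. Reproduce the protocol's own AF figures (section 9.5, THIN).** The protocol reports "among patients 18+ and register with GP for at least a year 1.92% (No. of patients with AF= 75784" and, after the valve exclusions, 74,319 or 1.89%.

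- Denominator implied by the AF figure: 75,784 / 0.0192 = 3,947,083. Rounding of 1.92% allows 75,784 / 0.01925 = 3,936,831 to 75,784 / 0.01915 = 3,957,389.
- NVAF prevalence over that range: 74,319 / 3,957,389 = 1.878% to 74,319 / 3,936,831 = 1.888%. The upper part of this range rounds to 1.89%.
- Removed by the valve exclusions: 75,784 − 74,319 = 1,465, or 1.9% of AF patients.

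The two figures agree with each other. They do not show how many patients qualify only through the tachycardia codes, and section 9.5 does not say whether Table S3 produced them.

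**5. Illustration only.** Suppose the 74,319 was drawn with Table S3, and a share s qualified only through the three codes. Both are assumptions. Then 74,319 × s patients leave and prevalence becomes 1.89% × (1 − s).

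| Assumed s | Patients leaving | Prevalence after |
|---|---|---|
| 0.5% | 372 | 1.88% |
| 1% | 743 | 1.87% |
| 2% | 1,486 | 1.85% |
| 5% | 3,716 | 1.80% |

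**6. Effect on a reported proportion.** If a share c of the NVAF group is misclassified, and the characteristic has frequency q among them and p among true NVAF patients, the reported value is (1 − c)p + cq, a shift of c(q − p). With c = 3% and a gap of 30 points, the shift is 0.03 × 30 = 0.9 points. As an upper bound for label accordance, take p = 10% and q = 100%. Then c = 0.5% gives 0.995 × 10 + 0.5 = 10.45%, and c = 3% gives 0.97 × 10 + 3 = 12.7%. None of these values of c, p or q comes from the documents.

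**The case against.** The best reply is that the mismatch may hardly matter. A patient with a tachycardia code and any AF code is classified correctly, and the documents give no count of patients with a tachycardia code alone. A shift of 0.9 points is small beside a 95% half-width of 1.96 × √(0.25/541) = 4.2 points in a group as small as the 541 naive apixaban users cited in section 9.5. This stands as a reason for a moderate rating. It does not remove the point: bias does not shrink as the pooled cohort grows, and small cells of Table 1 can move more.

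A second reply is that the line is arbitrary, since flutter-only codes are not named in the definition either. This stands in part: the text should say whether flutter is meant. But the list itself groups flutter with fibrillation under G573 and keeps G570 apart, so separating the tachycardia codes follows the coding structure.

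Third, AF may be under-recorded. Section 9.9 admits that hospital information may be missing, so some patients coded only with tachycardia could have AF. This also stands, and it is why a sensitivity analysis is better than dropping the broad list altogether.

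For the same reason, a reader should not infer that patients with only a tachycardia code most likely received the DOAC for another indication, or that misclassification is concentrated in such users. Nothing in the protocol shows either. Nor can a patient count be had by applying a percentage to the 541 + 1,589 + 741 = 2,871 naive users in section 9.5. They come from a separate CPRD study up to October 2014, whereas this study pools THIN and CPRD, runs to 2016 and includes non-naive users.

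**Conclusion.** The point holds as an inconsistency between the NVAF definition and the only list that implements it. Three of 24 codes admit a different arrhythmia, one such record suffices, and no later step catches it. This rests on the documents alone.

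The size of the effect is unknown and may be small. The list would admit patients without an AF record, but the documents do not show that a material number enter, or that any reported result is distorted by a given amount. All percentages in the illustrations are assumptions. The THIN counts in section 9.5 are affected only if they were drawn with this list, and no sample-size calculation depends on them. Severity: should be fixed.

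**What to change.** - Remove 3274.00, G570.00 and G570000 from Table S3 for the primary NVAF definition.
- If atrial flutter is intended, say so in section 9.1 and Table S2, so that text and list agree.
- Report, by index drug, how many patients qualify only through the tachycardia codes.
- Keep the broad list only as a labelled sensitivity analysis.
- If the THIN counts in section 9.5 used Table S3, restate them.

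The work is three lines in a code list, one sentence in each of two places, and one extra count, all possible before the extraction planned for March 2017. The price is a slightly smaller cohort and the possible loss from the primary analysis of a few true AF patients coded only as tachycardia. The sensitivity analysis would show whether that matters.
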